This study will also explore the potential reduction of severe COVID-19 mediated disease through: 1) reducing time from symptom detection to treatment initiation (i.e., comparing treatment initiation times among those who test positive for COVID-19 in this study to published literature), and 2) closely monitoring COVID-19 symptoms among those who contract the virus (i.e., again, comparing participants in this study to published literature). COVID-19 is a novel virus and we do not fully understand its impact on our patient population. This study will provide useful, granular information about the daily symptoms of and recovery from COVID-19 in cancer patients. Data from this study will be used to pursue NIH R01 funding to formally evaluate the effects of using mHealth technology to monitor symptoms and health risk factors and intervene in real-time.

B. Background and Significance

The severe acute respiratory syndrome corona virus 2 (SARS-CoV-2) outbreak in late 2019 has resulted in approximately 4.28 million confirmed cases of novel coronavirus disease (COVID-19), with over 292,000 confirmed deaths worldwide (as of May 13, 2020)[1]. The United States has reported the greatest number of cases across the world, with a total of 1.4 million new cases and over 83,000 attributable deaths as of May 13, 2020. Severe disease accounts for approximately 10% of cases and adds tremendous burden on limited medical resources and medical personnel.

Risk factors for severe disease are largely unknown, but clinical experience suggests that persons over age 65 with co-morbid conditions, such as immunosuppression from cancer or chemotherapy, place cancer patients in the “high-risk” group for severe manifestations of COVID-19 mediated disease [2]. Therefore, cancer patients are likely at increased risk for COVID-19 infection and may have a poorer prognosis. According to recent data, the risk of severe infection in cancer patients approaches 40% with up to a 20% mortality rate [3]. Thus, there is increased need for invasive ventilation and intensive care unit admission to circumvent rapid clinical deterioration in this population. Novel methods are needed to remotely monitor for SARS-CoV-2 infection and rapidly intervene to reduce morbidity and mortality in cancer patients exhibiting symptoms of the virus. Given evidence of poor outcomes in cancer patients, early intervention may significantly improve outcomes.

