participants completed 87% of all EMAs and received an intensive level of tailored smoking-cessation treatment messages (102 messages on average) over a 3-week intervention period. We found that the on demand app functions were used regularly and the app was well-liked (e.g., 97% would like to use the app in the future if they were to relapse, and 85% would refer their friends who smoke to use the app).[30] Analyses of EMA data revealed that urges to smoke were significantly reduced when tailored urge messages were delivered by the app, as compared to instances where other types of messages were delivered ($p<.001$).[32] We also found reductions in stress ($p=.021$) and cigarette availability ($p<.001$) following tailored stress and cigarette availability messages, compared to other types of messages.[32] A total of 20% of participants were biochemically-confirmed abstinent 12 weeks post-quit, [24] which is better than many interventions conducted with low SES smokers.[33-38] We recently completed a 3-armed pilot randomized clinical trial (i.e., Project Smart-T2; OUHSC IRB #7195) that compared the Smart-T2 app to standard in-person smoking cessation clinic care and the free NCI QuitGuide app. Smokers who attended a clinic based tobacco cessation program were randomized to groups and followed for 13 weeks (1 week pre-quit through 12 weeks post-quit). All participants were asked to complete EMAs on study-provided smartphones for 5 weeks. 84 participants were enrolled and 22% of Smart-T, 15% of QuitGuide, and 15% of in-person participants achieved biochemically verified 7-day point prevalence abstinence 12 weeks post-quit. Smart-T3 (R01CA221819; the 3.0 version of Smart-T) was recently funded by the NCI. Smart-T Alcohol (i.e., R34AA024584) is an ongoing alcohol use reduction app for homeless adults) and Link2Care (i.e., R01MD010733) is an ongoing smartphone-based case management intervention for homeless adults. These studies demonstrate the utility, feasibility, versatility, and high compliance rates of our innovative smartphone apps.

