All participants will be prompted to complete EMAs once per day during the 24-week study time period. If a participant contracts COVID-19, they will click the “COVID-19 Positive” button in the app. This action will cause the app to ask a different set of questions focused on enhanced monitoring COVID-19 symptoms for the next 21 days. At the end of 21 days, the app will return to daily prompts of the pre-COVID-19 EMAs. At the conclusion of the 24-week EMA period, participants will gain access to a new button in the app that will initiate the 24-week follow-up assessment (see Appendix). Participants will receive a daily alert from the app to click the “Final Survey” button in the app to complete the end of study assessment. The 24-week phone interview (or RedCap interview if a medical condition prevents them from being able to speak for long periods of time) will be scheduled at the baseline visit and the date/time of the call will appear at the top of the app home screen. A maximum of five phone call/text attempts and one mailed letter will occur over two-week period, before data from phone interview (or RedCap interview if a medical condition prevents them from being able to speak for long periods of time) will be considered unattainable. Those participants who were loaned a mobile phone to use during the study will be mailed a stamped envelope to return the phone and charger, or will be approached by study staff to reclaim the mobile device during a routine follow-up visit in the SCC chemo infusion clinic. Upon receipt of the smartphone and charging equipment, all equipment will be sterilized with alcohol-based sanitizer in accordance with current practice guidelines put forth by the Centers for Disease Control at the time it is returned by the study subject.

EMA completion rates, participant dropout, and feedback on the participant satisfaction survey will be used to evaluate feasibility of this type of mobile intervention in this population.

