Aim 1. We will examine the percentage of prompted daily surveys that are completed throughout the 24-week intervention period and the percentage of participants who report they are satisfied with monitoring and use of mHealth application at the end of the 24-week study period. We will compare participant characteristics (e.g., demographics, health behaviors) and outcomes between those who are satisfied with the app and monitoring versus those who are dissatisfied. We will observe via mHealth app patient health risk factors and readiness to change health risk behaviors in SCC cancer patients. We will compare participant characteristics using chi-square test or independent t-test, as appropriate. The follow-up phone call based qualitative interview (or RedCap interview if a medical condition prevents them from being able to speak for long periods of time) will access participant perceptions of each app feature and be recorded for transcription and analyzed using NVivo. Recordings will be transcribed by internal staff, Microsoft Transcribe, or by approved contractors with whom a Business Associates Agreement has been made. When using Microsoft Transcribe, all transcriptions will be reviewed by study staff. This information will be used to improve this type of symptom monitoring apps in future studies and interventions.

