Aim 2. We will examine participant characteristics among those who are and are not transitioned to an Aim 2 monitoring of vital signs and severity of COVID-19 symptoms. We will also examine participant characteristics and outcomes for those that require emergent intervention versus non-emergent intervention. Among those who undergo enhanced monitoring, we will use descriptive statistics to summarize the proportion of patients experiencing the following outcomes: manifestations of severe disease, treatment related toxicity, need for hospitalization, and COVID-19 related mortality. We will also compare outcomes and tolerability of enhanced self-monitoring for severe infection and compare rates of disease related morbidity and mortality to baseline rates published in the literature. We will evaluate participant satisfaction with the app and identify ways to improve this novel patient monitoring technology. We will perform logistic regression to determine the odds of experiencing primary outcomes, based upon baseline characteristics (e.g., sex, race/ethnicity, cancer stage/type). Kaplan-Meier survival curves and log-rank tests of homogeneity will be used to identify the survival functions, describing the time to resolution of symptoms based upon

demographic characteristics. Because COVID-19 is a novel virus and we do not fully understand its impact on our patient population, this study will provide useful, granular information about the daily symptoms of and recovery from COVID-19 in cancer patients.

Aim 3. No analyses proposed, as this is a collaboration aim.

N. Data and Safety Monitoring Plan

Data quality and integrity will be held to the highest standard to ensure accurate reporting and documentation of the objectives outlined in the proposal. The Institutional Review Board and the Office of Clinical Research will monitor data and safety monitoring. The institutional plan for data and safety monitoring for all trials funded by the NCI has been adopted by the University and will be utilized for conduct of our planned proposal.

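### Does comparing satisfied with dissatisfied participants at week 24 leave out deaths and non-reporters in a way that needs a change to Aim 1?

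*Combined protocol and SAP*

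**What the plan says.** Section M, Aim 1 begins with two feasibility quantities: the percentage of prompted daily surveys completed, and "the percentage of participants who report they are satisfied with monitoring and use of mHealth application at the end of the 24-week study period". It then compares participant characteristics and "outcomes between those who are satisfied with the app and monitoring versus those who are dissatisfied". The only tests named are for characteristics: "We will compare participant characteristics using chi-square test or independent t-test, as appropriate". No test is named for outcomes, and Aim 1 does not list them.

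Section D (Measures) fixes the timing. After the 24 weeks of daily surveys, "participants will gain access to a new button in the app that will initiate the 24-week follow-up assessment". A phone interview, with a RedCap alternative, is booked at baseline. It is given up as unobtainable after five call or text attempts and one letter. The same section says that "EMA completion rates, participant dropout, and feedback on the participant satisfaction survey will be used to evaluate feasibility".

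The clinical events are listed under Aim 2, in Section A and again in Section M: "manifestations of severe disease, treatment related toxicity, need for hospitalization, and COVID-19 related mortality". They are to be summarised among participants in enhanced monitoring, with no reference to satisfaction.

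**The concern.** The grouping variable is measured after the period in which outcomes occur. To be classed as satisfied or dissatisfied, a participant must be alive at week 24 and must answer. Someone who dies earlier is in neither group, so a comparison of mortality by satisfaction would show none against none whatever happened. Hospitalization and severe disease would be compared only among survivors who reported.

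A second worry concerns survivors. Section H lets participants stop app monitoring at any time. Those who stop because they dislike the app are the people the dissatisfied group should contain, yet they can be classified only if the interview reaches them. The dissatisfied group may be small, so its make-up could depend on who is missing from it. Satisfaction is part of the primary aim, and Section M says the interview findings will guide later apps. A distorted profile of dissatisfied users could therefore mislead that work.

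**Working it through.** The plan gives no power, precision or event figure for this comparison, and no derivation of 500, so there is no figure to reproduce. The check takes the two readings of *outcomes* in turn, then the size of the non-response problem.

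**Reading A: Aim 1 outcomes include the clinical events.** Section B states that "the risk of severe infection in cancer patients approaches 40% with up to a 20% mortality rate".

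- Deaths outside both groups = 500 × infected share × fatality. The infected share is not in the documents; assume 2% to 20%. At 20% fatality: 500 × 0.02 × 0.20 = 2, and 500 × 0.20 × 0.20 = 20.
- Share of severe cases removed by death: if the 20% is of all cases and every death was severe, 0.20 / 0.40 = 50%. If the 20% is of severe cases, it is 20%. The sentence does not say which.

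On this reading, the absence of deaths from both groups follows from the definition and needs no assumption about rates.

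**Reading B: Aim 1 outcomes are the feasibility and questionnaire measures.** Aim 1 in Section A concerns feasibility, ease of use and perceived utility. Table 1 repeats the smoking, health, quality-of-life, depression and anxiety, and alcohol questions at week 24. Those scores exist only for people who answer at week 24, so restricting to reporters loses almost nothing that could have been compared. Survey completion is known for everyone, but the satisfaction label is still missing for non-reporters.

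Reading B fits the text better. Mortality, hospitalization, toxicity and severe disease are named only under Aim 2, and no section proposes relating satisfaction to death.

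**Non-response among survivors.** The documents give no expected satisfaction rate for this app. The nearest figures, in Section C, concern a smoking-cessation app: "97% would like to use the app in the future if they were to relapse, and 85% would refer their friends who smoke". They measure willingness to reuse or refer, so they serve here only as a range *s* = 0.85 to 0.97.

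- Dissatisfied at full response: 500 × 0.15 = 75, or 500 × 0.03 = 15.
- Non-reporters outnumber the dissatisfied when the non-response rate *r* exceeds (1 − s) / (1 + (1 − s)): 0.15 / 1.15 = 13.0%, or 0.03 / 1.03 = 2.9%.
- At an assumed *r* of 25%: 125 unclassified, against 375 × 0.15 = 56 or 375 × 0.03 = 11 dissatisfied.

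These figures compare group sizes; they do not measure bias. Bias in the characteristics comparison needs differential reporting. Suppose a characteristic splits 500 in half, 80 of each 250 are truly dissatisfied (odds ratio 1.0), and 90% of the satisfied report (170 × 0.90 = 153 per half). All of these inputs are assumed.

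| Dissatisfied who report, by half | Counts | Observed odds ratio | p (uncorrected chi-square) |
|---|---|---|---|
| 30% and 60% | 24/153 and 48/153 | 0.50 | 0.011 |
| 40% and 50% | 32/153 and 40/153 | 0.80 | 0.40 |
| 45% and 45% | 36/153 and 36/153 | 1.00 | – |

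A material distortion needs a twofold difference in reporting. Nothing in the documents indicates one, or rules it out.

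**What an edit would alter.** The candidate edits are to name the outcomes, label the tests as conditional on a week-24 report, and add a no-report column. None alters the satisfied-versus-dissatisfied counts, odds ratios or p-values, so any bias in them stays. Leaving mortality out of the comparison would remove something the plan never clearly put in.

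**The case for a change.** The strongest opposing case is that the plan leaves *outcomes* undefined, that the disease outcomes it does list include death, and that an analyst could take Section M literally. These patients are on active cancer treatment and are not compensated, and the completion target is only above 50%, so loss before week 24 is foreseeable. Even with mortality set aside, the sickest are the least likely to report, which would affect a hospitalization comparison too. The remedy would be a few sentences and one table column.

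Much of this stands. Section M assigns non-reporters to no group, and the comparison is conditional on reporting. The phone and RedCap routes cannot recover deaths. But an analyst who tabulated deaths by week-24 satisfaction would see at once that the rows were empty for a structural reason. The Aim 2 mortality summary does not pass through satisfaction and is untouched.

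Loss among survivors is also less hidden than it seems. Dropout is itself a feasibility measure, staff contact low completers during follow-up, and the interview is separate from app use. The group sizes set against the number enrolled show how many are unclassified. Table 1 also lists an app-evaluation item among the EMA measures, apparently weekly. It could describe people who leave early, though Section M does not use it to form the groups.

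The low cost is not fully established either. The 16 chart-review items in Section E name neither death nor hospitalization. Section D does provide for COVID-19 data from health records, but that need not cover other deaths among non-reporters.

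**Conclusion.** No change to the plan is needed. The observation is accurate: the satisfaction comparison describes week-24 reporters, and deaths before the report fall outside both groups. It becomes an error only if Aim 1's unlisted outcomes include clinical events, and the plan names those under Aim 2 and analyses them without regard to satisfaction. On the more natural reading, most of the outcomes compared exist only for reporters.

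The residual is differential non-response in an unpowered descriptive comparison, which does not touch the completion criterion of more than 50% and on which no stated decision depends. Its size is not known: the illustrated odds ratios run from 1.00 to 0.50 as assumed reporting moves from equal to twofold different. Naming the outcomes and giving the number without a report (died, stopped, not reached) is detail that analysts can supply when reporting. It would help the reader but would not make the two-group comparison less biased. This view would change if Aim 1 were shown to intend a comparison of death or hospitalization by satisfaction.

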RESEARCH PROTOCOL OUTLINE

Title of Project: Mobile Health Study and Enhanced Symptom Monitoring to Prevent Severe Illness from COVID-19 in Cancer Patients

Principal Investigators: [name]., Department of OB/GYN
[name], Dept. of Family and Preventive Medicine

Co-Investigators: [name], College of Public Health

Abstract

The severe acute respiratory syndrome corona virus 2 (SARS-CoV-2) outbreak in late 2019 has resulted in over 4.28 million confirmed cases of novel coronavirus disease (COVID-19), with over 292,000 confirmed deaths worldwide (as of May 13, 2020). Severe disease occurs in ~10% of cases overall. However, risk for severe disease and mortality is greater in immunocompromised cancer patients, requiring scarce ventilation resources and intensive care unit space to address rapid clinical deterioration in this population. We propose to use the established Insight™ mHealth Platform, a component of the Stephenson Cancer Center (SCC) mHealth Shared Resource, to create the “Symptom Tracker” app. The Symptom Tracker (Insight™) app will enable real-time monitoring of cancer patient symptoms that are consistent with early signs of SARS-CoV-2 infection in this high-risk population by automatically (and securely) transferring this information to health care providers. The primary aim of this study is to determine the feasibility, ease of use, and perceived utility of this app to monitor symptoms and health risk behaviors among cancer patients currently receiving chemotherapy. Health risk behaviors, standard COVID-19 screening questions, and a single chemotherapy risk question will be assessed daily through the smartphone app. Specific responses will automatically trigger an alert to clinic nurses AND provide app-based access to contact the clinic for triage to home care or emergency assessment. When/if study participants screen positive for COVID-19, they will receive a device to measure their pulse and blood oxygen levels daily. This information and COVID-19 symptoms will be monitored daily via the Symptom Tracker (Insight™) app. This study will determine if an app can be used to rapidly report COVID-19 symptoms and quickly intervene to reduce morbidity and mortality in immunocompromised cancer patients. Further, data from this study will be used to inform the development of future mHealth interventions that will be tested in fully powered randomized control trials.

A. Specific Aims

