The primary objective of this research is to use innovative mHealth technology to monitor symptoms in real-time and facilitate medical triage of high-risk patients. The current study will obtain data on the feasibility of an innovative mHealth application to track symptoms and automatically intervene upon reported high-risk symptoms among cancer patients who are receiving cytotoxic chemotherapy or immunotherapy treatments. This objective will be attained by pursuing the following specific aims:

1. Determine the feasibility, ease of use, and perceived utility of the Symptom Tracker (Insight™) mHealth app to monitor symptoms and health risk behaviors for up to 500 patients who are receiving chemotherapy to treat cancer.
 - a. On average, participants will complete >50% of all prompted daily phone based ecological momentary assessments (EMAs).

- b. Most participants will report that the app is easy to use, and provides useful information (assessed quantitatively and qualitatively during the 24-week phone based or RedCap follow-up interview).
2. Examine participant characteristics and outcomes of those who do and do not test positive for COVID-19 during the 24-week monitoring period.
 - a. Among those who undergo enhanced monitoring, we will use descriptive statistics to summarize the proportion of patients experiencing the following outcomes: manifestations of severe disease, treatment related toxicity, need for hospitalization, and SARS-CoV-2 related mortality.
 - b. We will also compare outcomes and tolerability of enhanced self-monitoring for severe infection and compare rates of disease related morbidity and mortality to baseline rates published in the literature.
 - c. We will use quantitative and qualitative methods to evaluate participant satisfaction with the app among those who test positive for COVID-19 and are asked to report vital signs each day.
3. Collaboratively document and share lessons learned regarding the impact of the COVID-19 pandemic on cancer care delivery via telemedicine and mHealth technology. We commit to a collegial collaboration with other cancer centers funded to study the use of telemedicine through the COVID-19 CCSG supplement mechanism.

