As a practicing oncologist within Stephenson Cancer Center, [name], Ph.D. is knowledgeable about the medical needs of the population that is being recruited for this study, and she regularly uses evidenced-based interventions to treat cancer. Her research and clinical experience complement [name] experience with research using mobile technology for health improvement. Additional study investigators include [name] (biostatistician) and [name] (basic and translational scientist) have agreed to assist with study recruitment and follow-up procedures.

D. Research Design and Methods

Study Design: A total of 500 treatment-seeking males and females will be asked to complete daily monitoring of symptoms and weekly monitoring of health risk factors weekly via smartphone app (Aim 1). Those who screen positive for COVID-19 will be triaged to emergency or non-emergency medical treatment. COVID-19 positive patients identified for non-emergent medical treatment will receive a study-supplied device to measure their oxygen level and heart rate and be instructed in the device's use. They will be prompted to enter vital signs data daily (such as body temperature, oxygen level, and heart rate) and questions from the app will change to assess the severity of COVID-19 related symptoms and inform changes in level of care, to emergency or non-emergency medical management as indicated by self-reporting. The proposed study will assess the impact of heightened symptom and vital sign monitoring on the early identification of severe manifestations of COVID-19 in this high-risk population (Aim 2). It is hypothesized that this will significantly improve COVID-19 related morbidity and mortality compared to the national and international rates currently reported in the literature. Figure 1 displays the participant flow through this 24-week study.

The SCC mHealth Shared Resource has created the versatile and reusable Insight™ mHealth Platform. Insight™ is HIPAA compliant and data are encrypted within the app. There will be 4 sources of data for the current study: 1) in-person data collected in a private room at the SCC

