When participants provide a pattern of responses that are suggestive of heightened risk for COVID-19 (See algorithm in Appendix), they will receive a suggestion to contact SCC staff, and the app will send an encrypted email containing this information to [name] and other SCC staff with a request to contact the participant to assess symptoms (see Appendix) and whether urgent medical attention is indicated. Should urgent medical attention be warranted, the patient will be instructed to the clinical unit most appropriate to the symptoms they reported through the app algorithm or discussed with the clinical nursing or physician staff. Non-emergent patients who screen positive for COVID-19 will begin an enhanced symptom and vital sign monitoring period that will continue until the participant reports that they are no longer symptomatic and/or a medical professional informs them that they no longer need to self-quarantine, which is expected to be approximately 21 days. These patients will receive a pulse oximeter (provided by the study) and the app questions will change to include daily prompts requesting that the patient input morning vital signs (temperature, heart rate, blood oxygen levels (SpO2)) and answer questions specific to the severity of symptoms and/or emergence of new symptoms of COVID-19. If a patient is hospitalized, they can continue to complete the daily assessments if they are willing and able to do so. The app will also support check-ins with SCC staff and after-hours medical staff as needed after diagnosis of COVID-19 or until the patient has been medically released from self-quarantine. Once the participants have completed the enhanced symptom and vital sign monitoring portion of the study, the pulse oximeter will be returned to the research team at the time of their next scheduled appointment. These devices will then be sterilized with both alcohol-based sanitizing products as well as ultraviolet light exposure in accordance with practices endorsed by the Centers for Disease Control.

Participants will continue to use the app to complete a final 24-week follow-up survey and will be contacted by phone (or RedCap if a medical condition prevents them from being able to speak for long periods of time) to complete a brief qualitative interview 24 weeks after study enrollment. Relevant demographic, cancer-specific and COVID-19 related data will be extracted

from electronic health records at the conclusion of the study.

E. Chart Review

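### Aim 2 asks about participants who do and do not test positive, but section M compares those who do and do not enter enhanced monitoring and never states the test-result contrast

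*Combined protocol and SAP*

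**What the plan says.** Section A sets Aim 2 by test result: "Examine participant characteristics and outcomes of those who do and do not test positive for COVID-19 during the 24-week monitoring period". Section M, under Aim 2, groups differently: "We will examine participant characteristics among those who are and are not transitioned to an Aim 2 monitoring of vital signs". That sentence covers characteristics only. The next sentence of section M compares patients needing emergent with those needing non-emergent intervention, on characteristics and outcomes. Nowhere does section M state a comparison of positive with not-positive participants.

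The documents describe entry to enhanced monitoring in two ways.

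- **Restricted to non-emergent positives.** Section D, Study Design: "Those who screen positive for COVID-19 will be triaged to emergency or non-emergency medical treatment", and then "COVID-19 positive patients identified for non-emergent medical treatment will receive a study-supplied device to measure their oxygen level and heart rate". Section D, Study application: "Non-emergent patients who screen positive for COVID-19 will begin an enhanced symptom and vital sign monitoring period".
- **Open to any positive.** Abstract: "When/if study participants screen positive for COVID-19, they will receive a device to measure their pulse and blood oxygen levels daily". Section D, in the text after Table 1, says of a participant pressing the app's positive-result button: "This action will cause the app to ask a different set of questions focused on enhanced monitoring COVID-19 symptoms for the next 21 days". Neither sentence carries a non-emergent condition.

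**The concern.** If entry is restricted, a participant with COVID-19 who is sent to emergency care at first triage is not transitioned and is counted with the uninfected. That misplacement depends on severity. The case group loses its sickest members at triage, and any characteristic related to severity is over- or under-represented among those who remain. A reader of the results would take the table as an answer to Aim 2, when it partly describes how patients were triaged.

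If entry is open to all positives, the groups lie closer to Aim 2, but membership then depends on the participant pressing a button. Either way the aim's own question has no matching analysis.

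**Working it through.** The plan gives no infection rate, emergent share, effect size, alpha or power, so it has no figure to reproduce. The check is expected-value algebra under the restricted reading.

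**1. General result.** Let RR be the true risk ratio for infection. Let e1 and e0 be the shares of positives who are emergent at first triage, with and without the factor. The risk of being transitioned is the infection risk times (1 − emergent share), so

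apparent RR = RR × (1 − e1)/(1 − e0).

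| e0 | e1 | (1 − e1)/(1 − e0) | True RR | Apparent RR |
|---|---|---|---|---|
| 10% | 40% | 0.60/0.90 = 0.667 | 1.5 | 1.00 |
| 10% | 40% | 0.667 | 1.0 | 0.67 |
| 20% | 60% | 0.40/0.80 = 0.50 | 1.5 | 0.75 |
| 30% | 70% | 0.30/0.70 = 0.429 | 2.0 | 0.86 |
| 40% | 40% | 1.00 | 2.0 | 2.00 |

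The 10% and 40% are the severe-disease proportions quoted in section B for all cases and for cancer patients. They are not triage shares and serve only as rough anchors; the other shares are assumed. Reversal of a harmful association requires RR < (1 − e0)/(1 − e1). If e1 < e0 the multiplier exceeds 1 and the bias is upward.

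**2. Cost when shares are equal.** Assume N = 500, factor prevalence 40%, infection 10% without the factor, RR 2.0 and two-sided alpha 0.05. Grouping by test result gives OR 2.25 with power about 87%. Grouping by transition with e0 = e1 = 40% gives OR 2.14 with power about 65%. The direction is kept, but power is lost.

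**3. Worked example.** N = 500 is from the plan; all else is assumed: 50 infected, factor in 40% of the 450 uninfected (180) and in 50% of the infected (25). The true OR is (25/25)/(180/270) = 1.50. Let E be the number emergent at first triage and q the share of them with the factor.

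- Transitioned: (25 − qE)/(50 − E)
- Not transitioned: (180 + qE)/(450 + E)

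With q = 70%:

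| E (share of positives) | Transitioned | Not transitioned | OR |
|---|---|---|---|
| 10 (20%) | 18/40 = 45.0% | 187/460 = 40.7% | 1.19 |
| 15 (30%) | 14.5/35 = 41.4% | 190.5/465 = 41.0% | 1.02 |
| 20 (40%) | 11/30 = 36.7% | 194/470 = 41.3% | 0.82 |

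**4. Sensitivity to q**, for E = 10, 15, 20:

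- q = 60%: OR 1.33, 1.23, 1.11 (attenuation only)
- q = 50%: OR 1.49, 1.48, 1.47 (almost no change)
- q = 30%: OR 1.85, 2.15, 2.64 (inflation)

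At a 10% emergent share (E = 5) with q = 70%, the OR is 1.35.

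**5. Sampling error.** Using the log-OR standard error √(1/a + 1/b + 1/c + 1/d), the correct grouping (50 vs 450) gives 1.50 with 95% CI 0.84 to 2.69. The 0.82 has 95% CI 0.38 to 1.77.

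**The case against.** The strongest reply is that the abstract and the app description let every positive participant into enhanced monitoring. Study application also allows hospitalized patients to continue daily assessments, and section M summarises hospitalization and mortality among those under enhanced monitoring. On that reading, being transitioned is close to reporting a positive result and most of the bias goes. This stands as a limit on the bias. It does not rescue the analysis, because Study Design and Study application say otherwise and the test-result contrast is still missing.

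A reader might infer that emergent patients certainly fall into the comparison group, or that any characteristic tied to severity is pulled towards or past no association. The documents do not support either. The first depends on which entry wording applies, and concerns only patients emergent at first triage; those who worsen after entry stay in the transitioned group. The second is false in general: a factor unrelated to infection moves away from the null, and a factor linked to milder disease is inflated.

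It is also fair that the reversal rests on chosen inputs, that neither grouping would settle the example factor at this sample size, and that the primary aim is feasibility, with no decision rule attached to this comparison. The emergent versus non-emergent comparison would partly reveal the selection, but it has no uninfected group and so does not supply the missing contrast.

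**Conclusion.** The mismatch between Aim 2 and section M is certain from the text: the stated contrast is absent and another stands in its place. The meaning of the substitute is unsettled, because the documents contradict themselves on who enters enhanced monitoring, and those passages must be reconciled.

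The bias is conditional. It arises if entry is restricted to non-emergent positives and the emergent share differs by the factor studied, and it can run in either direction. In the illustration it ranges from an OR of 0.82 to 2.64 against a true 1.50, depending on the assumed emergent share and on the factor's prevalence among emergent cases. These figures show what the grouping can do; they do not predict what this study would find. The point is worth correcting because the change is small and the analysis as written does not answer its aim.

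**What to change.** In section M, Aim 2, make the main contrast: characteristics and outcomes of participants who do and do not have a positive SARS-CoV-2 test during the 24 weeks, with the result taken from the app report and confirmed in the health record. Report positives in two subgroups, emergent and non-emergent at first triage. Keep transitioned versus not transitioned only to describe who reached enhanced monitoring. Separately, reconcile the entry wording in the abstract and the three places in section D. The test-result contrast holds whichever wording is kept.

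The cost is one or two sentences and a little more analysis. The data need confirming: Study application promises extraction of COVID-19 related data, but the list printed in section E shows neither test result nor triage status and refers to an appendix for the full list. The sponsor should confirm that both items are collected.
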